5.2. Trial Rationale

Opioid drug use disorder is a major health and social issue and is a chronic medical condition that often requires long-term maintenance treatment. An important aim of the treatment programs for opioid drug dependence is to assist in helping the patients stop abusing illicit drugs. Further important aims are to improve their mental and physical health, as well as their social conditions. This can be achieved by increasing patients' quality of life and will also reduce the burden on the society and relatives. Moreover, opioid addicts often inject with used syringes and

needles, and thus expose themselves to high risk of transmission of infectious diseases, including human immune deficiency virus (HIV) and hepatitis C.

Opioid maintenance treatment, such as SL BPN, is one of the most effective treatment options available for opioid dependent drug users and is associated with substantial reductions in illicit opioid use, criminal activity, deaths, and HIV transmission (6). Patients often discontinue treatment prematurely, an outcome associated with higher rates of relapse to drug use, which means that treatment strategies that aim to keep patients in treatment longer and/or improve patient adherence may have additional advantages (7). While daily dosing with SL BPN has proven effective, the need for daily administration of treatment may negatively influence patients' adherence and duration of therapy. Moreover, SL tablets or film can be easily abused and diverted for illicit use, injected for greater effect, or accidentally ingested, especially by children (7, 8). The limitations associated with SL BPN are of particular relevance to patients who have children at home, to those who have difficulty making frequent visits to the physician's office (e.g., patients in remote locations, those with limited mobility, or those who travel frequently) or to those who have difficulty managing the responsibility of daily dosing.

During initiation of treatment with BPN, some patients do not actually take the SL tablets dispensed to them, and they may also request doses that are higher than necessary in order to potentially abuse or divert the extra doses (9). In this regard, CAM2038 q1w is ideal for initiation as it can't be abused or diverted by patients and may help prevent patients from requesting medically unnecessary doses, giving clinicians greater control over what the patient actually needs and receives. CAM2038 q1w is available in multiple doses, thereby permitting flexibility in dosing options and allowing for weekly visits during the initial stages of treatment to provide clinicians with the opportunity to optimize and individualize treatment for each patient.

In addition to the above mentioned potential advantages, CAM2038 q1w demonstrated more stable concentrations with less peak-trough fluctuation over 7 days as compared with daily doses of SL BPN. Moreover, the bioavailability of BPN administered as CAM2038 q1w is approximately 7-fold that of SL BPN products. The pharmacokinetic profile of CAM2038 q1w indicates that a rapid and long-acting release of BPN should lead to rapid and smooth onset of action, in combination with a prolonged and stable treatment effect in opioid dependent patients with control of withdrawal symptoms for at least 7 days following a single dose. Notably, the pharmacokinetic profile of CAM2038, with a smooth and stable release of BPN and time to peak plasma concentrations within the first 24 hours after dosing, mimics a typical SL BPN titration schedule with low but increasing starting doses of SL BPN or BPN/naloxone tablets during the first 24 to 48 hours, followed by more constant dosing. Patients who have recently used opioids and are not in withdrawal at the time of BPN ingestion or who have taken a long-acting opioid too recently, may experience precipitated withdrawal with onset of BPN treatment. The primary motivation behind the initial 4 mg incremental titration schedule in the present trial is to follow current guidelines that recommend gradually introducing patients to an appropriate maintenance dose of BPN while minimizing the risk of precipitated withdrawal. CAM2038 q1w provides this slow increase in plasma levels without the potential compliance and diversion issues associated with taking multiple SL tablets during the day. Thus, the pharmacokinetic profile of CAM2038 q1w may help to improve tolerability during treatment induction (including potentially reducing the probability of withdrawal symptoms in individuals with residual full opioid agonist). This

possibility has been supported in a previous clinical trial (Trial HS-07-307) in opioid dependent patients where the pharmacokinetic profile of CAM2038 q1w was associated with decreased subjective and clinical opiate withdrawal scores (Subjective Opiate Withdrawal Scale [SOWS] and COWS), over at least 1 week. Both SOWS and COWS scores were sustained below the limit of “mild” symptoms for the majority of patients up to and beyond 7 days after a single SC dose. Similarly, the mean time to first intake of rescue BPN medication was 10 days after a single dose of CAM2038 q1w.

Patients in greater stages of withdrawal or those who have a lesser degree of physical dependence at onset of initiation may experience agonist effects of BPN during initiation. Although less than full agonist opioids, BPN may nonetheless be associated with euphoria and other opioid-like effects, even in opioid-dependent individuals (10-12). Thus, for some patients, use of CAM2038 q1w, with its more gradual onset, may result in lower peak euphoria and other desirable effects that can be associated with the relatively rapid and defined peak in plasma concentrations associated with SL BPN. The potential for reducing these lingering desirable effects of BPN may help patients start the recovery process in a more optimal way than with current SL BPN treatments.

Generally, stabilization of opioid maintenance treatment with BPN begins after initiation with BPN and is usually completed within 1 to 2 months, when the patient is not experiencing withdrawal symptoms, is experiencing minimal or no side effects, and no longer has uncontrollable cravings for opioid agonist. During the stabilization phase, dose adjustments and frequent contact with patients increase the likelihood of compliance and successful treatment outcomes. Therefore, weekly assessment is usually indicated to make necessary dose adjustments. The profile of CAM2038 q1w provides an alternative to SL BPN products during this phase with potential added benefits of obtaining consistent and stable plasma levels of BPN, taking away the need to take daily medications, and helping to prevent diversion and accidental pediatric exposures during initial phases of opioid maintenance treatment.

Similarly, pharmacokinetic results indicate that CAM2038 q4w produces consistent and stable plasma levels over 4 weeks with flexible and multiple dosing options. These results suggest that CAM2038 q4w may be an effective and safe BPN formulation for delivery of relatively constant levels of BPN over one month. Monthly visits and injection are regarded as a suitable frequency for stabilized patients on BPN maintenance treatment. Therefore, CAM2038 q4w is considered as a promising alternative to current daily medications for BPN maintenance treatment of patients with opioid use disorder who have been stabilized and qualify for monthly visits for BPN therapy.

Overall, features of CAM2038 q1w and q4w may increase patient compliance relative to daily SL BPN dosage forms, and may help prevent treatment noncompliance in higher-risk patients (i.e., those patients who take “drug holidays” from their BPN when they wish to abuse illicit opioids). In addition, CAM2038 q1w and q4w may provide significant potential for reducing risks of diversion, abuse, and accidental pediatric exposure, which continue to be important public health consequences of SL BPN therapy.

Therefore, the purpose of this trial is to demonstrate the efficacy and safety of CAM2038 (q1w and q4w) as an office-based therapy for initiation and continuation of opioid maintenance treatment with BPN in patients with opioid use disorder.

5.3. Benefit – Risk Assessment

BPN is a substance with well-established use for treatment of opioid drug dependence. The CAM2038 products contain BPN in a new FC formulation for SC injection. Clinical trials have demonstrated effectiveness of BPN in reducing illicit opioid use and improving retention rates of patients in outpatient maintenance treatment of opioid dependence, as well as substantial reduction in criminal activity, deaths, and HIV transmission. The need for daily administration of SL BPN may negatively influence patients' compliance and BPN tablets or film can be easily diverted for illicit use, injected for greater effect, or accidentally ingested, especially by children.

CAM2038 q1w and CAM2038 q4w are ready-to-use, SC BPN FC Injection depots that are being developed as substitution treatment of opioid drug dependence, and provide extended BPN release at target plasma concentrations over the weekly and monthly dosing intervals, respectively. Due to the fact that CAM2038 products need to be administered by a clinician, CAM2038 products cannot be abused or diverted by patients. In addition, it may help preventing patients from requesting unnecessarily high BPN doses, and it will provide clinicians greater control over what the patient actually needs and receives. Compared with the SL BPN products on the market, CAM2038 q1w and CAM2038 q4w have several potential advantages: 1) Rapid therapeutic onset (with maximum plasma concentrations established within 24 hours after injection) followed by steady long-acting release, 2) Reduced variation in BPN plasma levels over time (stable plasma levels attained for at least 28 days [CAM2038 q4w] and 7 days [CAM2038 q1w]) resulting in more consistent therapeutic plasma levels and a possible reduction in morning "cravings", 3) Less frequent dosing resulting in reduced frequency of clinic visits and need for medical support, 4) Significantly higher bioavailability, meaning less drug substance in circulation and on the street, 5) Decreased risk of drug diversion, and 6) Easier dose adjustment.

To date, three Phase I/II clinical trials (HS-07-307, HS-11-426 and HS-13-487) have been conducted in both opioid dependent and healthy volunteers under naltrexone block. The safety profile of CAM2038 q1w and CAM2038 q4w is comparable to reference SL BPN approved treatment and good local tolerability was demonstrated with findings limited to only a few cases of transient, mild, local inflammation, pruritus and/or injection site pain.

A number of potential AEs can be associated with the administration of long-acting depots. The most severe side-effects specific for the investigational product that may occur are related to local reactions at the site of injection after SC administration and include dermal ulcers or necrotic wounds at the injection site. Additional potential AEs include over-dose of BPN and allergy to BPN. There is also a potential risk of local obstruction and blockage at the injection site with accidental intravascular injection

Systemic repeated toxicity for up to 4 months of once-weekly SC administration of CAM2038 q1w and once-every-4-week administration of CAM2038 q4w in dogs showed absence of systemic toxicity by assessment of complete clinical pathology, histopathology and toxicokinetics. The treatment related findings were limited to reversible clinical effects

compatible with known pharmacological effects of BPN (reduced activity, ataxia, sporadic salivation, and intermittent soft feces, as well as reduction in body weight and food consumption) and to local, transient injection site findings, characterized as foreign body response. No novel toxicological aspects arose for BPN in the CAM2038 drug product formulations in comparison with available information on the drug substance alone. Absence of systemic toxicity has also been shown for up to chronic SC exposure of the FC system in rodents and non-rodents. The local toxicity findings at the injection site following SC administration of the CAM2038 drug products in a large number of non-clinical studies were described by necropsies and histopathology as a reversible local continuum of an inflammatory response consistent with the physiological inflammatory reactions occurring in response to the injection of an insoluble material.

The current protocol is intended to evaluate the efficacy of CAM2038 q1w and q4w by demonstrating non-inferiority of CAM2038 in BPN treatment compared to SL BPN in adult outpatients with opioid use disorder. The safety monitoring practices employed by this protocol are adequate to protect the patients' safety and should detect all treatment-emergent AEs.

The approximate volume of blood is 94 mL for each subject over the course of the entire trial (Screening to End of Treatment (EOT) visit), but not including repeat or additional tests ordered by the Investigator) and presents no undue risk to the subjects.

Therefore, CAM2038 q1w and q4w may provide alternative treatment options that potentially can increase patient compliance relative to daily SL BPN dosage forms, and may help prevent treatment noncompliance in higher-risk patients (i.e., those patients who take "drug holidays" from their BPN when they wish to abuse illicit opioids). In addition, CAM2038 q1w and q4w may provide significant potential for reducing risks of diversion, abuse, and accidental pediatric exposure, which continue to be important public health consequences of SL BPN therapy.

The available information suggests that the present clinical trial has a favorable benefit-risk ratio.

6. TRIAL OBJECTIVES

6.1. Primary Objective

The primary objective of the trial is:

- To demonstrate non-inferiority of the CAM2038 BPN treatment arm as compared to the SL BPN treatment arm in treating adult outpatients with opioid use disorder, as measured by the primary efficacy measure of response rate (RR).

6.2. Secondary Objectives

The secondary objectives of the trial are:

- To demonstrate non-inferiority of CAM2038 compared to SL BPN in adult outpatients with opioid use disorder, as measured by the secondary efficacy measure of percentage negative urines.
- To evaluate the efficacy of CAM2038 compared to SL BPN in adult outpatients with opioid use disorder, as measured by the secondary efficacy measure of time to sustained abstinence from illicit opioid use.
- To evaluate the efficacy of CAM2038 compared to SL BPN in adult outpatients with opioid use disorder, as measured by the secondary efficacy measure retention rate.
- To evaluate the efficacy of CAM2038 compared to SL BPN in adult outpatients with opioid use disorder, as measured by the exploratory efficacy measures.
- To evaluate the safety of CAM2038 in adult outpatients with opioid use disorder.

7. INVESTIGATIONAL PLAN

7.1. Overall Trial Design and Plan

This is a randomized, double-blind, double-dummy, active-controlled, parallel group multi-center trial, designed to evaluate the non-inferiority of CAM2038 compared to an existing standard of care (SL BPN) in initiation and maintenance treatment with BPN. The trial will involve 4 phases: Screening, Phase 1 (weekly visits), Phase 2 (monthly visits), and Follow-up.

Following Screening and confirmation of eligibility, subjects will be randomized to one of two treatment groups in a 1:1 ratio:

- Group 1: SL BPN tablets + placebo SC injections
- Group 2: CAM2038 SC injections + SL placebo tablets

Following randomization, subjects will undergo initiation of BPN with either SL BPN or SC CAM2038 q1w and participate in weekly visits for 12 weeks (Phase 1). After Week 12, subjects will be transitioned to Phase 2 with monthly visits. During Phase 2, subjects in Group 1 will continue treatment with monthly dispensing of daily SL BPN treatment and monthly placebo SC injections, and subjects in Group 2 (receiving CAM2038 q1w) will be transferred to monthly injections of CAM2038 q4w and monthly dispensing of daily SL placebo. Subjects will participate in up to 6 visits during the 12 weeks of Phase 2; 3 scheduled monthly visits and 3 random urine toxicology visits. At each visit, efficacy and safety outcome measures will be assessed. After Phase 2, the subjects will be followed-up for 1 month.

A total of 20 opioid urine toxicology samples will be collected during the study:

- 1 sample at Screening
- 1 sample at baseline (Day 1/Week 1) before first dose of CAM2038 q1w
- 12 samples will be collected at the scheduled 12 weekly visits of Phase 1 (Week 2 to Week 13 [i.e. 1 week after the last CAM2038 q1w treatment])
- 6 samples will be collected during the 12 weeks of Phase 2
 - 3 at the scheduled monthly visits (Weeks 17, 21 and 25)
 - 3 at random urine toxicology visits (taken during the period from Week 13 to Week 25).

A self-report of drug use will accompany every urine toxicology test as outlined in Table 3 and Table 4. Each subject will participate in the trial for up to 31 weeks, including up to 24 weeks of treatment with SL BPN or CAM2038. Subjects who complete the 24 weeks of treatment will be transitioned to standard of care (e.g., SL BPN) and be followed up for 4 weeks.

All subjects will be blinded to their treatment group assignment, as will all trial staff with the exception of the clinician(s)/staff performing the SC injections and designated personnel who will be responsible for drug accountability (i.e., counting the active and placebo SL BPN returned tablets).

To ensure adequate enrollment and address potential inconvenience to subjects, all subjects (regardless of randomized group) will receive appropriate compensation for time and travel expenses related to attendance at trial visits. All costs of medications and counseling will also be covered.

Investigators will be instructed to use manual-guided psychosocial counseling for trial subjects throughout the trial period.

An overview of the trial design is provided in Figure 3.

Section 10 provides additional information on the baseline, efficacy and safety assessments included in the trial. Efficacy and safety variables are described in Section 10.6 and the statistical analyses are described in Section 12.

[figure not shown]

Figure 3 Overview of Trial Design

BPN = buprenorphine; R= randomization; SL = sublingual

7.1.1. Screening Visit (Week -3 to Week -1)

Medical and eligibility screening will occur within 3 weeks of the first day of Phase 1 (Day 1). At Screening, subjects will provide written informed consent to participate in the trial before any protocol-specified procedures or assessments are completed.

The Screening visit will include standard medical screening procedures, complete medical/psychosocial history, urine toxicology and detailed substance use and treatment history, as outlined in Table 3.

Following Screening, subjects will be eligible for further participation if they meet all of the inclusion criteria and do not meet any of the exclusion criteria.

7.1.2. Phase 1 (Weekly Visits)

Week 1 (Initiation of Treatment):

Eligible subjects will be initiated on BPN treatment, during which time they will attend trial visits at the site as needed based on their withdrawal symptoms. Prior to Day 1, subjects will be instructed to arrive at their Day 1 visit in a state of mild withdrawal, to avoid precipitated withdrawal with BPN.

A flow chart summarizing induction procedures is provided in Figure 4.

Day 1: On Day 1, after confirmation that subjects are in at least mild state of withdrawal, subjects will have an ECG performed as well as have their vitals taken. Subjects will then receive a test dose of unblinded 4 mg SL BPN film under observation prior to randomization to confirm tolerability by assessing signs and symptoms of precipitated withdrawal as measured by COWS.

One (1) hour, after tolerability has been confirmed and eligibility criteria have been re-checked, subjects will be randomized to one of two groups in a 1:1 ratio:

- Group 1 (SL BPN): Daily SL BPN + placebo SC injections
- Group 2 (CAM2038): CAM2038 SC BPN injections + daily SL placebo

After randomization, subjects will receive the following, while on site:

- A blinded dose of 4 mg SL tablets (active or placebo) will be administered under observation. Thus, the total Day 1 SL BPN dose is 8 mg (4 mg unblinded BPN film + 4 mg blinded BPN tablets) for Group 1 and 4 mg (4 mg unblinded BPN film) for Group 2.
- A single CAM2038 q1w (once-weekly) 16 mg SC injection (0.32 mL of active or placebo) will be administered.
- After receiving the first dose of study medications, the ECG and vitals will be repeated.
- If withdrawal symptoms are still not relieved after the second SL dose on Day 1, symptomatic relief with non-opioid medications should be provided.
- Subjects will be instructed to return to the clinic on Day 2 for observation and Day 2 dosing.

Day 2 and Day 3: All subjects will return to the clinic only on Day 2 for an additional observed dosing of SL BPN/Placebo to ensure continued tolerability. All subjects will receive 16 mg SL BPN/Placebo (two 8mg SL BPN or placebo tablets).

Administration of Day 2 SL BPN/Placebo dose will be observed in the clinic.

Subjects will also be provided with Day 3 take-home dose (two 8 mg SL BPN/Placebo tablets per day).

Day 4: All subjects will return to the clinic on Day 4 and will receive a single CAM2038 q1w 8 mg or Placebo SC injection (0.16 mL of active or placebo). In situations where the visit cannot occur on Day 4 due to logistical constraints, the visit may occur one day early or one day late (+/- 1 day). However, it is strongly encouraged to have the subject return on Day 4.

[figure not shown]
All subjects will continue with the 16 mg SL BPN/Placebo (two 8mg SL BPN or placebo tablets per day). This may be observed in the clinic or be taken at home.

Subjects will be provided with adequate amount of SL BPN/Placebo tablets for take-home to last through Day 7.

Days 5 to 7: All subjects will be allowed to return to the clinic through an Unscheduled Visit, if continued withdrawal symptoms are present. During Days 5 to 7, one additional SC injection (CAM2038 q1w 8 mg or Placebo – not to exceed total weekly dose of CAM2038 q1w 32mg or placebo) and increase in SL BPN/Placebo dose may be provided (not to exceed 24 mg SL BPN/Placebo per day).

Additional outcomes measures and procedures to be performed at each visit are outlined in Table 3.

Week 1 CLINIC VISIT FLOW CHART

Day 2

- All subjects will return on Day 2 for observations on tolerability/safety and observed dosing for SL BPN/Placebo (16 mg SL BPN/Placebo).
- Subjects will be provided take home dose of 16 mg SL BPN/Placebo for Day 3.

Day 4

- All subjects return to the clinic on Day 4 for an additional CAM2038 q1w 8 mg SC or Placebo SC injection.
- All subjects will receive 16 mg SL BPN/Placebo daily to take home for Days 4-7 (Day 4 can be taken in the clinic or be taken at home).

Day 5-7

- All subjects will be instructed to return to the clinic if their withdrawal symptoms are not adequately controlled. Subjects that are not adequately controlled should receive additional SL BPN/Placebo (not to exceed 24 mg or 3 tabs/day) and one additional CAM2038 q1w 8 mg or placebo SC injection.

Figure 4 Overview of Induction Procedures

BPN=buprenorphine; SC=subcutaneous; SL=sublingual

On Day 2, subjects will be provided with SL tablets and instructions for dosing. The daily SL BPN/Placebo dose for Days 2-4 will be 16 mg and the maximum daily SL BPN/Placebo dose for Days 5-7 will be 24 mg.

Weeks 2 to 12:

Day 8 (Week 2): All subjects will return to the clinic on Day 8.

Subjects will receive a CAM2038 q1w SC injection (24 mg or 32 mg or Placebo, based on total dose given by end of Week 1/Day 7). Subjects will also be provided with one-week take-home SL BPN/Placebo (16 mg, or 24 mg SL BPN/Placebo, based on total daily dose established at end of Week 1/Day 7 (the take home medication will be provided in 7 count bottles of 8 mg tablets)). If subject is still experiencing withdrawal symptoms on Day 8, the Investigator can increase the dose to a maximum of 24 mg per day SL BPN/Placebo and a 32 mg injection of CAM2038/Placebo.

Week 3 to Week 12: From Week 3 to Week 12, at minimum subjects will attend weekly scheduled visits. At each scheduled visit, a SC injection of CAM2038 q1w (or placebo) will be administered. The scheduled visit should be at the beginning of each week (± 2 days), preferably Mondays (see Section 10.3.1). During these visits, additional dose adjustments will be allowed (increases and decreases). At each weekly visit, sufficient SL tablets (BPN or placebo) will be dispensed to last until the next visit. Dosage adjustments are given in 8 mg increments for both SL BPN and SC CAM2038 and can only be done at scheduled clinic visits. Total daily dose of SL BPN/Placebo cannot exceed 24 mg/day. Total weekly dose of CAM2038/placebo q1w cannot exceed 32 mg injection per week.

Weekly visit assessments will include:

- Urine samples for opioid toxicology, evaluated using both qualitative and quantitative methods. Urine will also be tested for other drugs of abuse using qualitative methods.
- Self-reported use of all drugs, including illicit or prescription opioids and other prescribed or illicit drugs.
- Measures of withdrawal using COWS and SOWS
- Measures of craving using Desire to Use and Need to Use visual analogue scales (VAS)
- Psychosocial counseling
- Additional outcomes measures and safety assessments for each visit, as outlined in [Table 3](#).

At each weekly visit, starting at Week 5, the subjects will be evaluated with regard to the following stability criteria:

- Has the subject been on a stable dose of CAM2038 q1w/Placebo SC injections without any fluctuations in doses for the last 4 weeks?
- Does the subject exhibit minimal subjective and no objective withdrawal symptoms, based on SOWS ≤ 7 and COWS < 5 ?
- Does the subject exhibit diminished desire/need to use, based on VAS scores?
- Does the subject exhibit diminished use of illicit opioids, according to the Investigator's discretion?

The results of the evaluations will be recorded for data collection purposes, but no subject will be transitioned to monthly dosing before Week 13.

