9.1.1. Phase 1 (Weekly Visits)

Week 1:

On Day 1, all subjects will have an ECG and vital signs recorded, and after confirmation of a mild state of withdrawal, a test dose containing 4 mg/1 mg BPN/naloxone (SL film) will be administered under observation. If tolerability to the test dose is shown, subjects will be randomized to Group 1 or Group 2 and will receive the following treatments in Week 1 during Phase 1:

- Group 1:
 - On Day 1, the subjects will receive a total dose of 8 mg SL BPN (4 mg SL BPN film and 4 mg SL BPN tablets) and a total dose of 0.32 mL placebo CAM2038 (matching 16 mg active CAM2038 q1w).
 - On Days 2 and 3, the subjects will receive a daily dose of 16 mg SL BPN.
 - On Day 4, the subjects will receive 16 mg SL BPN and an SC injection of 0.16 mL placebo CAM2038 (matching 8 mg active CAM2038 q1w).
 - On Days 5 to 7, the daily dose of SL BPN will be 16 to 24 mg and the subjects may receive an additional SC injection of 0.16 mL placebo CAM2038.
 - The total Week 1 dose of placebo CAM2038 must not exceed 0.64 mL (matching 32 mg active CAM2038 q1w).
- Group 2:

- On Day 1, the subjects will receive a total dose of 4 mg SL BPN (4 mg SL BPN film and 4 mg SL placebo tablets) and a total dose of 16 mg active CAM2038 q1w (0.32 mL).
- On Days 2 and 3, the subjects will receive a daily dose of 16 mg SL placebo.
- On Day 4, the subjects will receive 16 mg SL placebo and an SC injection of 8 mg active CAM2038 q1w (0.16 mL).
- On Days 5 to 7, the daily dose of SL placebo will be 16 to 24 mg and the subjects may receive an additional SC injection of 8 mg active CAM2038 q1w (0.16 mL).
- The total Week 1 dose of active CAM2038 q1w must not exceed 32 mg (0.64 mL).

Weeks 2 to 12:

- Group 1: Daily SL BPN tablets (containing BPN and naloxone) up to a daily dose of 8 mg to 24 mg (doses from 8 mg/2 mg to 24 mg/6 mg) and weekly SC injections of placebo CAM2038 of 0.32 mL, 0.48 mL or 0.64 mL (matching 16 mg, 24 mg and 32 mg doses of active CAM2038 q1w) per week.
- Group 2: Daily SL placebo tablets (tablets matching 8 mg/2 mg to 24 mg/6 mg doses) and weekly SC injections of active CAM2038 q1w BPN at doses of 16 mg, 24 mg or 32 mg (0.32 mL, 0.48 mL or 0.64 mL) per week.

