ⁱ It is the Investigator’s responsibility to understand and comply with all laws and regulations that apply to HIV, Hepatitis B, and Hepatitis C and testing of blood. Hepatitis B/C and HIV testing is required unless a site’s IRB prohibits such testing.

Trial Period/Phase:	Screening	Phase 1 (Weekly Visits)							
	Month:	-1	M1				M1-3		
	Week:	-3 to -1	W1				W2-W11		W12
	Day:	-21 to -1	D1 ^a	D2	D3	D4	D5-7	D8	Weekly ^b
Dispense Treatment Identification Card		X							
Urine Toxicology	X	X					X	Weekly	X
Illicit Drug Use Self-Report	X	X					X	Weekly	X
SOWS, COWS, VAS ^j	X	X	X		X	(X)	X	Weekly	X
C-SSRS ^k	X	X	X		X	(X)	X	Weekly	X
Measurement of Morning Desire to Use/Need to Use							X	Weekly	X
SL BPN or SL placebo dispensing		X	X		X	(X)	X	Weekly	X
SL BPN or SL placebo administration ^l		X	X	X	X	Daily	X	Daily	X
CAM2038 q1w or placebo SC injection ^m		X			X	(X)	X	Weekly	X
Psychosocial Counseling		X					X	Weekly	X
Adverse Events ⁿ	X	X	X		X	(X)	X	Weekly	X
Concomitant Medications/Procedures	X	X	X		X	(X)	X	Weekly	X
On-site visits	X	X	X		X	(X)	X	Weekly	X

Abbreviations: BMI=body mass index; BPN=buprenorphine; COWS=Clinical Opiate Withdrawal Scale; C-SSRS=Columbia Suicide Severity Rating Scale; D=day; DSM-V= Diagnostic and Statistical Manual of Mental Disorders – Fifth Edition; ECG=electrocardiogram; HIV=human immunodeficiency virus; M=month; SC=subcutaneous; SL=sublingual; SOWS=Subjective Opiate Withdrawal Scale; VAS=visual analogue scale; W=week (X) indicates as needed based on the individual subject.

^j SOWS/COWS/VAS will be completed each time the subject visits the clinic, as needed based on titration and dosage adjustment. On Day 1, COWS, SOWS and VAS will be completed before the test dose is administered (baseline). COWS will also be completed after the test dose on Day 1 to evaluate tolerability, and on Day 2.

^k Screening version at Visit 1 (Screening), Since Last Visit version at all subsequent visits.

^l Not to exceed 24 mg SL BPN (or placebo) per day, this administration will be done at home.

^m Not to exceed 32 mg CAM2038 q1w (or placebo) per week.

ⁿ Any spontaneously reported adverse event will be recorded after the subject signs the informed consent form. In addition, adverse events will be elicited using a non-leading question each time the subject visits the clinic.

Table 4 Schedule of Assessments: Phase 2 (Monthly Visits) and Follow-up

Trial Period/Phase:	Phase 2 (Monthly Visits)						Follow-up			
	Month:	M4		M5		M6		M7		

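### Early Phase 1 sublingual tablet supplies stop short of the last permitted visit day: clearly after Day 2, and arguably after Day 4 and Day 8

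*Protocol*

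**What the plan says.** **Day 2 supply.** Protocol 7.1.2 says: "Subjects will also be provided with Day 3 take-home dose (two 8 mg SL BPN/Placebo tablets per day"). Figure 4 repeats it: "Subjects will be provided take home dose of 16 mg SL BPN/Placebo for Day 3".

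**Day 4 visit.** If logistics prevent attendance on Day 4, "the visit may occur one day early or one day late (+/- 1 day"), although Day 4 is strongly encouraged. Section 9.1.1 (Group 1) sets the dose: "On Day 4, the subjects will receive 16 mg SL BPN and an SC injection of 0.16 mL placebo CAM2038". Tablets for Days 4 to 7 are handed out at this visit.

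**Day 8 visit.** Section 7.1.2 says: "Subjects will also be provided with one-week take-home SL BPN/Placebo" at 16 or 24 mg per day, and "the take home medication will be provided in 7 count bottles of 8 mg tablets". It states no window for Day 8.

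**Weekly visits.** The paragraph for Weeks 3 to 12 gives a window of plus or minus 2 days. It also has sites dispense, at every weekly visit, enough tablets to carry the subject to the next one. Table 3 footnote b gives the same window but for weekly visits in Weeks 2 to 12, and Day 8 is labelled Week 2. Footnote l, on SL dosing, reads: "Not to exceed 24 mg SL BPN (or placebo) per day, this administration will be done at home". Section 9.2.2 describes the Phase 1 supply simply as weekly.

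**The concern.** Where a visit window has a late edge, the supply from the preceding visit should reach it. Otherwise a subject can follow every instruction and still have no tablets. Here the fixed quantities match the nominal visit dates and not the permitted range.

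The two arms are affected differently. In Group 1 the tablets carry all the buprenorphine. In Group 2 they are placebo and the depot supplies the drug, although the next injection is then late as well. A supply gap therefore interrupts active treatment in the SL BPN arm while dose is still being established. At stake are continuity of dosing and patient safety in the first weeks.

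**Working it through.** **Reproducing the plan's own figure.** The Day 8 supply is stated as one week in bottles of seven 8 mg tablets.
- 16 mg/day: 16 / 8 = 2 tablets a day; 2 x 7 = 14 tablets = 2 bottles = 7 days.
- 24 mg/day: 24 / 8 = 3 tablets a day; 3 x 7 = 21 tablets = 3 bottles = 7 days.

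Both agree with one week.

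**Formula.** Uncovered doses = (day of next visit - 1) - last supplied day, or 0 if negative. The dose on the day of the late visit counts as covered by that visit.

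**Inputs.** Day 8 is Week 2, so Week 3 is nominally Day 15.
- Day 2 supply: last supplied day 3; next visit Day 3 to Day 5.
- Day 8 supply: last supplied day 14 if the Day 8 dose comes from the bottle, 15 if it comes from clinic stock; next visit Day 13 to Day 17.
- Day 4 supply: last supplied day 7; next visit Day 8 under 7.1.2, or Day 6 to Day 10 if footnote b applies.

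**Results.**

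| Supply | Latest next visit | Calculation | Uncovered doses |
|---|---|---|---|
| Day 2 | Day 5 | (5 - 1) - 3 | 1 (Day 4) |
| Day 8, dose from bottle | Day 17 | (17 - 1) - 14 | 2 (Days 15, 16) |
| Day 8, dose from clinic stock | Day 17 | (17 - 1) - 15 | 1 (Day 16) |
| Day 4, if Day 8 has a window | Day 10 | (10 - 1) - 7 | 2 (Days 8, 9) |

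On-time attendance gives zero in every row.

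**How firm each row is.**
- Day 2: both statements of quantity name Day 3 only, and the late edge is explicit. In Table 3 the row "SL BPN or SL placebo dispensing" is marked on Days 2 and 4 but not Day 3. That is consistent, but the table shows nominal days and gives no quantities, so it adds little.
- Day 8: the fixed one-week quantity competes with the weekly dispensing sentence in the next paragraph. If that sentence governs Day 8, there is no gap.
- Day 4: sections 7.1.2 and Table 3 differ on whether Day 8 has a window. Without one, there is no gap.

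**Tablets needed.**
- After Day 2, for Days 3 and 4: 2 x 2 = 4, against 2 now.
- After Day 8, for Days 8 to 16 (9 days): 9 x 2 = 18 or 9 x 3 = 27, a surplus over 14 or 21 of 4 or 6 for an on-time subject. In whole bottles, 3 x 7 = 21 or 4 x 7 = 28, a surplus of 7 either way.
- After Day 4, only if Day 8 has the window: 2 more days, 4 tablets at 16 mg/day or 6 at 24 mg/day.

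**The case against.** The strongest defence is that the literal reading is too strict. Day 8 falls under the Weeks 2 to 12 heading, so the weekly dispensing rule can be taken to cover it, with one week and the bottle size describing only the nominal supply. This stands as a fair alternative, and it is why the Day 8 gap is called ambiguous.

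For Day 2, the text after Figure 4 says tablets are given that day and states one daily dose for Days 2 to 4. Day 5 attendance is an exception, and a site that foresees it can plan. But that text gives no quantity, while two other sentences do, and both stop at Day 3. This gap stands.

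Symptom-driven visits in Week 1 (7.1.2) and unscheduled visits (10.3.6) offer a partial way back to the clinic, but neither tells a site to supply for a late visit. The Manual of Procedures may settle quantities; it was not available. Tight supply also has a purpose, since section 5.2 names diversion of extra doses during initiation.

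A reader might infer more than the documents support:
- *That the gap biases the primary comparison.* The responder criteria (Protocol 12.3.2.1, SAP 9.1) use Weeks 10 to 13 and the Phase 2 samples. SAP 9.1.1 mentions the Weeks 2 to 13 samples, but no criterion tests one before Week 10. Any path through early dropout is indirect, and no late-visit rate is given.
- *That subjects would go into withdrawal.* Section 9.7 says dissociation from the receptors may take several days after SL BPN stops.
- *That Tables 1 and 2 can size the loss of exposure.* They come from healthy volunteers, they mix trials for the weekly depot, and steady state cannot be assumed on Day 3. No symptom threshold is given to interpret a ratio.

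**Conclusion.** The point holds as a cheap improvement. One gap is clear: a Day 5 visit leaves the required Day 4 dose unsupplied, which in the SL BPN arm means no active drug that day. Two are conditional: up to 2 doses before a Day 17 visit (1 if the Day 8 dose comes from clinic stock), provided the one-week Day 8 quantity is fixed; and 2 doses before a Day 10 visit, provided footnote b gives Day 8 a window. Only subjects who attend late within the window are affected.

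The counts assume that the stated quantities are what sites dispense and, for the Week 3 gap, that the Week 2 visit takes place on Day 8. No effect on response, withdrawal rate or retention is shown. SAP 9.3.3 uses urine samples from Week 3 as an exploratory measure, but any effect there is unquantified.

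**What to change.** Extend the dispensing rule now placed under Weeks 3 to 12 to the Day 2, Day 4 and Day 8 visits, and define the next visit as its scheduled date plus the allowed late window.

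- Day 2: give 4 tablets, for Days 3 and 4.
- Day 8: give 18 tablets at 16 mg/day or 27 at 24 mg/day.
- State whether Day 8 has a window. If it does, supply through Day 9 at the Day 4 visit, and count the Day 8 supply from the actual visit date.
- Align section 9.2.2 with the rule.

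The cost is wording in the protocol and Manual of Procedures, plus kit counts. On-time subjects hold 2 surplus tablets after Day 2 and 4 to 7 after Day 8; if Day 8 has a window, also 4 or 6 after Day 4. This is a modest diversion risk, limited by the return of unused drug under section 9.2.1. If surplus is the greater worry, give the extra only to subjects expected to attend late, or arrange a top-up collection. That avoids most of the surplus but relies on foreseeing the delay or adds a visit.
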